#### 11.2. Statistical analysis plan

Categorical variables will be expressed as percentages and numbers and will be compared using the Chi-square or Fisher's exact test. Continuous variables will be presented as means, standard deviations, medians, and interquartile ranges and will be compared using an independent two-sample t-test or Wilcoxon rank sum test, while the normality of the underlying variable distribution will be estimated using histograms, skewness, kurtosis, and the Kolmogorov-Smirnov test.

The primary outcome will be presented and compared between the two groups using an independent two-sample t-test. Normality of the empirical distribution of the primary outcome will be evaluated. If this assumption is violated, a nonparametric Wilcoxon rank-sum test will be used. Secondary outcomes will also be summarized and compared between groups using independent two-sample t-tests for continuous outcomes, or chi-square test or Fisher's exact test for categorical outcomes. Considering the factors that may influence the outcome, aside from the randomly assigned intervention, we will conduct an analysis involving the adjustment of the baseline characteristics for primary and secondary outcomes. This careful analytical strategy ensures that our findings are not confounded by pre-existing differences, thereby allowing us to assess the true impact of the intervention more accurately. A planned, exploratory subgroup analysis will be performed to compare the treatment effect in patients with vericose veins with and without Entelon® medication. Unless otherwise specified, all tests will be performed at a significance level of 0.05. All analyses will be performed using SAS 9.4 (SAS Institute Inc., Cary, NC, USA). Statistical support will be provided by [name].

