symptomatic improvement by lower extremity venous Doppler ultrasonography at 6 and 12 weeks post-treatment follow-up. Patients with Varicose Vein of Lower Extremity Prolonged venous reflux time (superficial vein ≥ 0.5 sec, deep vein ≥ 1 sec) (N=200) Randomization Vitis Vinifera Extract (Entelon®) + Therapeutic lifestyle changes only Therapeutic lifestyle changes (N=100)(N=100)Primary endpoint: Change in venous reflux time from baseline to 6, 12 weeks Secondary endpoint: improvement of venous veflux (superficial vein < 0.5 sec, deep vein < 1 sec) Change from baseline to 6, 12 weeks in vessel diameter, venous reflux volume, clinical status by VCCS, CIVIQ-14 Inclusion 1) Adult males and females aged between 19- and under 80-years-old 2) Patients with the following findings on venous Doppler ultrasound criteria examination: - Superficial veins (such as the great saphenous vein, small saphenous vein, etc.) showing venous reflux for 0.5 seconds or longer - Deep veins (such as the femoral vein, etc.) showing venous reflux for 1 second or longer 3) Patients who have completed the washout period as described below by Visit 2, including the screening period: - Analgesics, steroids, anti-inflammatory drugs, and venoactive medications (such as Entelon®, etc.): at least 4 weeks 4) Patients who voluntarily provide written informed consent to participate in this clinical trial **Exclusion** 1) Peripheral arterial occlusive disease in the lower limbs criteria 2) Asymptomatic lower extremity varicose veins 3) Acute deep vein thrombosis 4) Frequent lower limb pain due to neuropathy 5) Patients who have undergone or are scheduled for varicose vein procedures/surgeries (However, patients who have undergone a procedure or surgery more than 1 year prior to the screening date are eligible to participate.) 6) Patients diagnosed with systemic diseases causing edema or thrombosis, heart failure. endocrine diseases such as (hypothyroidism, Cushing's syndrome, uncontrolled diabetes), allergic reactions to medications, urticaria and angioedema,

malabsorption and protein-calorie malnutrition, obstructive sleep apnea, or thrombophilia, as determined by the investigator

- A. History of malignancy within the past 5 years, but the following cases are eligible for clinical trial participation:
- B. Those who have a history within the past 5 years but maintain a cured state without recurrence or metastasis

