#### 7. Research Procedures and Evaluation

#### 7.1. Visit 1 (Screening Visit, Weeks 4 to 2 at randomization)

Participants will visit the study site within 2–4 weeks before the study to receive an explanation of the study, provide informed consent to participate, and undergo the screening tests described below.

Patients with clinically significant abnormalities at this time will be excluded from the study.

- 1) Assignment of screening numbers: Screening numbers will be assigned according to the order in which written consent is received
- 2) Review of patient medical history and demographic information
- 3) Review of inclusion/exclusion criteria eligibility
- 4) Measurement of vital signs, height, and weight
- 5) Assessment of existing medications
- 6) Performance of blood tests and urinalysis
- 7) Performance of lower extremity venous Doppler ultrasound imaging: Patients with confirmed venous reflux times of 0.5 seconds in the bilateral superficial veins and 1 second or more in the deep veins

8) Assessment of symptoms: Venous Clinical Severity Score (VCSS), CIVIQ-14

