## 11. Data Analysis & Statistical Considerations

#### 11.1. Sample size calculation

This is an exploratory study to determine the effectiveness of medication in improving venous reflux in patients with varicose veins, and there are limited prior studies to draw upon. Therefore, the study design is based on some assumptions, and it is not advisable to apply the same process to calculate the number of participants that are required to meet the mathematical basis for a confirmatory study when controlling for type 1 and type 2 errors.

Nevertheless, a few assumptions can be made to develop a power-calculation process similar to that of a confirmatory study. According to the literature, the duration of reflux was measured slightly differently at each point, and we calculated the number of participants based on the GSV, prox, which had the largest number of patients (Reference: J Vasc Surg. 2004 Aug;40(2):303-10.). In this study, we examined the difference between the means, but we could not find any evidence; therefore, we used the median value of the references as the mean. This assumes that n is sufficiently large (174), according to the principle of the central limit theorem, so the gap between the median and mean is not large. We also calculated the standard deviation using the range and number of n. By calculating the standard deviations of the other parameters together, we found that the standard deviation of the valve-carrying segments can be assumed to be approximately 1.8 overall. The results of the drug group are expected to improve by approximately 10% to 15%; therefore, we decided to conservatively assume an improvement of 12.5% to calculate the number of participants.

Valve-carrying	n	Median (s)	Range (s)	sd
segment				
GSV, prox	174	6.1	0.7-10.0	1.737
GSV, dist	84	3.5	0.7-10.0	1.921
SSV	91	4.6	0.6-10.0	1.918

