In this case, assuming a normal distribution and based on a Z-test with the same variance in both groups, the following calculation result was obtained under  $\alpha$ =0.025,  $\beta$ =0.2. The calculations were performed using the PASS15. A one-tailed test was performed to determine superiority if the difference between the drug and lifestyle treatment groups was less than zero. Assuming that patients may drop out during the study, the dropout rate was set at 20% to account for dropouts in a typical clinical setting. Therefore, the total number of participants was calculated as 160, with 80 participants in each group. Considering a dropout rate of 20%, we plan to recruit 200 participants, 100 in each group, to conduct the study.

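### Make ANCOVA on the Visit 1 reflux time the primary analysis, and state that 80% power on a change score assumes a correlation of about 0.5

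*Combined protocol and SAP*

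**What the plan says.** The study design figure in section 1 gives the primary endpoint as "Change in venous reflux time from baseline to 6, 12 weeks"; section 3.3 gives the same endpoint for the target vessel. For its analysis, section 11.2 states: "The primary outcome will be presented and compared between the two groups using an independent two-sample t-test". A Wilcoxon rank-sum test replaces the t-test if normality fails. Later in section 11.2 the plan adds that "we will conduct an analysis involving the adjustment of the baseline characteristics for primary and secondary outcomes", with no model, no list of covariates and no statement of its rank beside the t-test.

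Section 11.1 opens with "This is an exploratory study to determine the effectiveness of medication in improving venous reflux" and then sizes the trial "assuming a normal distribution and based on a Z-test with the same variance in both groups". The calculation printed in section 1 compares mean reflux times of 5.3 and 6.1 s, a difference of 0.8 s. On the SD, section 11.1 says "We also calculated the standard deviation using the range and number of n" and concludes that "the standard deviation of the valve-carrying segments can be assumed to be approximately 1.8 overall". The source is a table of reflux times by vein segment in a cited study.

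The pre-treatment value is already collected: section 7.1 lists "Performance of lower extremity venous Doppler ultrasound imaging" at Visit 1, and sections 7.3 and 7.4 require the scan again at Visits 3 and 4.

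**The concern.** Two linked points arise.

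- **Analysis.** A t-test on change uses the Visit 1 value only by subtraction, which fixes its coefficient at 1. ANCOVA estimates that coefficient from the data. In a randomized trial both are valid, but ANCOVA is at least as precise in large samples. The sentence on adjustment does not fill the gap, because the model and covariates could still be chosen after the data are seen.
- **Sample size.** The SD of 1.8 s describes how single reflux times vary. The endpoint is a change, and its SD depends on how strongly baseline and follow-up values correlate. The plan gives neither an SD of change nor a correlation, so its 80% power rests on an assumption that it does not state.

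At stake is the chance of detecting the effect that the trial was sized for. Bias and error control are not in question.

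**Working it through.** **Inputs.** From sections 1 and 11.1: 80 evaluable patients per arm, difference 0.8 s, SD 1.8 s, one-sided alpha 0.025, target power 80%. Rho is not in the documents, so a range is shown. The SD is taken as 1.8 s at both times.

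**1. The plan's own figure.** Standard error = 1.8 × √(2/80) = 0.2846. 0.8 / 0.2846 = 2.811. Power by the z-test = Φ(2.811 − 1.960) = 0.8026, as printed in section 1. Dropout: 80 / 0.8 = 100 per arm. Both reproduce. This is power for comparing two single measurements with SD 1.8 s.

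**2. SD under each analysis.**

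- Change score: SD = 1.8 × √(2(1 − rho)). This equals 1.8 when 2(1 − rho) = 1, so rho = 0.5.
- ANCOVA: residual SD = 1.8 × √(1 − rho²).
- Variance ratio, ANCOVA to change score: (1 − rho²) / (2(1 − rho)) = (1 + rho)/2, which is below 1 for every rho below 1.

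**3. Power and sample size.** Noncentral t distribution, with 158 degrees of freedom for the t-test and 157 for ANCOVA:

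| rho (assumed) | SD of change | Power, t-test | n per arm for 80% | ANCOVA SD | Power, ANCOVA | n per arm for 80% |
|---|---|---|---|---|---|---|
| 0.2 | 2.277 | 60% | 129 | 1.764 | 81% | 78 |
| 0.3 | 2.130 | 66% | 113 | 1.717 | 83% | 74 |
| 0.4 | 1.972 | 72% | 97 | 1.650 | 86% | 68 |
| 0.5 | 1.800 | 80% | 81 | 1.559 | 90% | 61 |
| 0.6 | 1.610 | 88% | 65 | 1.440 | 94% | 52 |
| 0.7 | 1.394 | 95% | 49 | 1.285 | 97% | 42 |
| 0.8 | 1.138 | 99% | 33 | 1.080 | 99.6% | 30 |

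The t-test reaches 80% at rho 0.503, or at 0.497 by the plan's z-test.

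**4. If the SDs differ.** Let the follow-up SD be k × 1.8. The variance of change is 1.8²(1 + k² − 2k·rho), so its SD equals 1.8 at rho = k/2: 0.40 for k = 0.8 and 0.60 for k = 1.2. Change variance minus ANCOVA variance is 1.8²[1 + k² − 2k·rho − k²(1 − rho²)] = 1.8²(1 − k·rho)². This is never negative, so ANCOVA's advantage does not depend on equal SDs. The break-even value does.

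**5. Mixed target vessels (illustration only).** Section 8.5 allows several vessels. Assume the segments are mixed 174:84:91 as in the table of section 11.1, with medians 6.1, 3.5 and 4.6 s taken as means and a within-segment SD of 1.8 s. The between-segment variance is then 1.180, and ANCOVA without a vessel term has 75 / 78 / 82 / 87 / 92 / 97 / 99.6% power at the seven values of rho. With a vessel term it returns to the ANCOVA figures in the table above. The change score is unaffected, because the segment mean cancels.

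**The case against.** The strongest reply is that this is more a preference than a defect. The t-test is valid, a change score already uses each patient's own starting value, and the study calls itself exploratory. If rho is 0.7 or 0.8, the gain is only 95 to 97% or 99 to 99.6%. All of that stands, and it limits how heavily the point should weigh. It does not remove the point, because the plan still states 80% power and a superiority test, and the better analysis needs no new data.

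A second reply is that section 11.2 already promises adjustment, and baseline reflux time is a natural covariate. This is partly right: what remains is to name the model, the covariate and its primary status.

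Third, the absolute power figures are soft:

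- At rho 0.5, the SDs tabulated in section 11.1 (1.737 to 1.921 s) move t-test power from 83% to 74%.
- The stated 12.5% improvement is 0.125 × 6.1 = 0.7625 s, not 0.8 s, and gives 76% at rho 0.5.
- The mixed-vessel illustration leaves out the deep veins, borrows another study's mix and applies 0.8 s to every segment. If the effect were 12.5% of the mixed mean of 5.08 s, about 0.64 s, power at rho 0.5 would be about 60% for the change score and 73% for ANCOVA with a vessel term.

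These change the levels but not the ordering of the two methods.

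Finally, no section says how the target vessel is chosen, and the schedule in section 14 labels Visit 2 as baseline although no scan is done there. Both gaps affect a change score as much as an ANCOVA.

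**Conclusion.** The concern holds. The plan's primary test is the less precise of two valid analyses of the same data, and its adjusted analysis is neither specified nor primary. The 80% power applies to the planned change score only if rho is about 0.5 or higher. Below that the t-test falls short (66% at rho 0.3); above it the plan exceeds 80%. ANCOVA has at least 81% power throughout rho 0.2 to 0.8.

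These figures rest on an SD of 1.8 s at both times, a 0.8 s effect, 80 evaluable patients per arm, and one vessel type or a vessel term in the model. The advantage of ANCOVA is a large-sample result, which is safe at about 160 patients. Under-power is not shown, since rho is unknown. The change should be made, but the trial's validity does not depend on it.

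**What to change.** In section 11.2, replace the primary test with wording such as:

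> The primary analysis is an ANCOVA of week-12 venous reflux time of the target vessel, with treatment arm and the Visit 1 reflux time of the same vessel as covariates, and a term for vessel type if target vessels are mixed. The adjusted mean difference is reported with its 95% confidence interval.

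Use the same form for week 6 and for continuous secondary endpoints that have a baseline value. Keep the unadjusted t-test and the Wilcoxon test as sensitivity analyses. Week 12 is used here because it is the end visit. The plan lists weeks 6 and 12 without choosing, so that choice is a separate decision for the investigators.

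In section 11.1, state that 1.8 s is the SD of a single measurement and that 80% power for a change score assumes rho of about 0.5 with equal SDs, or show power for rho from 0.2 to 0.8.

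The cost is wording in sections 11.1 and 11.2 and one degree of freedom, with no new patients, visits or scans. The target vessel also needs a definition, but the present change score needs that too.

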#### 3.3. Primary endpoint

Change in venous reflux time [Time Frame: 6, 12 weeks]: We will assess the changes in venous reflux time of target vessel using lower-limb venous Doppler ultrasound examinations.

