#### 7.3. Visit 3 (Midterm Assessment Visit, 6 weeks from randomization visit)

- 1) Lower extremity venous Doppler ultrasound (required)
- 2) Assessment of symptoms: Venous Clinical Severity Score (VCSS), CIVIQ-14
- 3) Performance of blood tests, urinalysis (optional)
- 4) Concomitant medications check (antiplatelet, antithrombotic, antihyperlipidemic).
- 5) Review of lifestyle therapy frequency of stocking wear, pharmacotherapy medication adherence checks
- 6) Monitoring of adverse events

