#### 10.2. Handling of stops and dropouts

In the event of discontinuation or withdrawal from the study, the principal investigator or person in charge shall discontinue the administration of the investigational drug and record the date of discontinuation and withdrawal, reason for discontinuation and withdrawal, along with all data obtained up to the time of discontinuation and withdrawal in the supporting documents and CRF. In particular, if the patient does not visit the clinic during the study, the reason for and future progress will be followed up through e-mail, telephone, etc., and progress will be recorded in the CRF. The results of the clinical trial obtained up to the time of discontinuation or dropout may be reviewed for evaluable items during the final evaluation.

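### Reflux time is measured at weeks 6 and 12 but tested with a two-sample t-test, so a week-12 comparison ignores the week-6 scans of patients who miss week 12 and is open to bias if dropout differs by arm

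*Combined protocol and SAP*

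**What the plan says.** The research summary defines "Primary endpoint: Change in venous reflux time from baseline to 6, 12 weeks", and section 3.3 gives the same two time points. Neither ranks them. Sections 7.3 and 7.4 make the Doppler examination mandatory at both visits.

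For the analysis, section 11.2 states: "The primary outcome will be presented and compared between the two groups using an independent two-sample t-test". If normality is violated, a Wilcoxon rank-sum test replaces it. The section adds that "we will conduct an analysis involving the adjustment of the baseline characteristics for primary and secondary outcomes", without naming the characteristics or describing a model over visits.

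On missing data, section 11.1 says "the dropout rate was set at 20% to account for dropouts in a typical clinical setting". Section 10.2 adds only that "The results of the clinical trial obtained up to the time of discontinuation or dropout may be reviewed for evaluable items during the final evaluation". The document gives no imputation rule, analysis set or missing-data assumption.

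**The concern.** A two-sample t-test takes one value per patient. Applied at week 12, it uses only patients scanned at week 12. Someone scanned at week 6 who then leaves contributes nothing to that comparison, although the week-6 value carries information about the likely week-12 value.

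Two things could be at stake. One is efficiency, because data already collected are left out of the week-12 estimate. The other is bias. If those who leave differ in week-6 response from those who stay, and differ in one arm more than in the other, the patients left at week 12 are no longer comparable between arms.

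That pattern is plausible here. Assignment is open (section 4.2) and only one arm receives the drug (sections 4.3 and 4.4). The withdrawal grounds in section 10.1 include non-compliance, treatment taken outside the physician's direction and a change in condition. Each of these could follow early response and could differ by arm.

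**Working it through.** **Inputs from the documents.** Difference 0.8 s, SD 1.8 s, one-sided alpha 0.025, 80 per arm evaluable, 20% dropout, 100 per arm randomised (section 11.1 and the sample size output in section 1).

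**Assumed, because the documents do not give them.** The correlation r between the week-6 and week-12 changes; the share of dropouts who have a week-6 scan; and how strongly dropout depends on week-6 response.

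**1. The plan's own figure.**
- n per arm = 2(1.960 + 0.842)² × 1.8² / 0.8² = 79.5, so 80.
- SE at 80 per arm = 1.8 × √(2/80) = 0.2846. Power = Φ(0.8/0.2846 − 1.960) = Φ(0.851) = 0.8026, as stated.
- 80 / (1 − 0.20) = 100 per arm, as stated.

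A week-12 test on those who complete, with 20% random dropout, therefore has the planned 80.3% power.

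**2. What a repeated-measures model would add under random dropout.** If m of the 20 dropouts per arm have a week-6 scan, the variance of the week-12 arm mean is SD² × [(1 − r²)/80 + r²/(80 + m)]. The effective n is the reciprocal of the bracket.

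| r | m = 10: effective n, power | m = 20: effective n, power |
|---|---|---|
| 0.5 | 82.3, 81.3% | 84.2, 82.2% |
| 0.7 | 84.6, 82.4% | 88.7, 84.1% |
| 0.8 | 86.1, 83.1% | 91.7, 85.3% |

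The gain over 80.3% is about 1 to 5 points.

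**3. Bias at week 12 when selection acts in one arm only.** Take r = 0.7, with all 20 dropouts per arm scanned at week 6 and dropout in the other arm unrelated to response. Bias = (shift in the mean week-6 value among stayers, in SD units) × r × 1.8.
- *Mild selection, 1 log-odds per SD.* With logistic dropout averaging 20%, the shift is 0.173 SD, so bias = 0.173 × 0.7 × 1.8 = 0.22 s. If exactly 20 patients are drawn, with selection weights rising by a factor of e per SD, simulation gives 0.24 s.
- *Upper limit, exactly the 20 worst leave.* The shift is φ(0.842)/0.80 = 0.280/0.80 = 0.350 SD, so bias = 0.350 × 0.7 × 1.8 = 0.44 s.

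**4. Direction and consequence.**
- *Poor responders leave control.* A true 0.80 s appears as about 0.56 s under mild selection and 0.36 s at the limit. Simulated power is about 51% and 28%.
- *Poor responders leave the drug arm and the drug has no effect.* With 0.24 s bias, one-sided type I error is approximately Φ(−1.960 + 0.24/0.2846) = Φ(−1.117) = 0.13; simulation gives 0.14, against a nominal 0.025. The logistic version gives about 0.11 to 0.12.
- *Equal selection in both arms.* The simulated difference stays at 0.80 s, so there is about no bias.

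**5. Using week 6.** In the same simulations, an estimate that regresses week 12 on week 6 within arm recovers 0.80 s in each case. For r from 0.5 to 0.8 with logistic dropout at 1 log-odds per SD, the one-arm bias of the t-test is 0.15 to 0.25 s, and the model-based estimate stays within 0.01 s of the truth.

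**The case against.** **The sample size already allows for dropout.** This stands. A reader might infer that the trial is underpowered because week-6 data are left out. The documents do not support that: 80 per arm remain after 20% loss, and the planned power is kept. What is forgone is a modest gain that depends on assumed quantities.

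**The plan does not discard week-6 data.** This also stands in part. A reader might infer that these values are never used. The endpoint covers both visits, so they would enter a week-6 comparison, which later dropout cannot bias. Section 10.2 also leaves room to review them. But that sentence is permissive and is not an analysis rule; the choice would be made after the data are known.

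**Dropout related to response need not bias a t-test.** Correct. The tempting statement that the t-test is unbiased only when dropout is unrelated to week-6 response is too strong, since equal selection in both arms cancels. The documents contain no evidence that dropout will differ by arm. Control patients are not untreated either: they receive lifestyle measures, including compression stockings. Open assignment makes differential dropout plausible but does not establish it.

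**The drug effect would simply be understated.** The documents do not support a single direction. The reverse pattern inflates the false-positive rate.

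**The ultrasound assessor is blinded (section 8.5).** That protects the measurement, but not who stays in the trial.

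**The trial is called exploratory, and a mixed model assumes normal residuals.** The first carries limited weight, because section 11.1 sets alpha and power and describes the test thus: "A one-tailed test was performed to determine superiority if the difference between the drug and lifestyle treatment groups was less than zero". The second is fair. The source data in section 11.1 range from 0.6 to 10.0 s, so skewness is possible and the Wilcoxon test should keep a role.

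**Conclusion.** The concern holds in a limited form. Section 11.2 names a one-value-per-patient test for an outcome measured twice, and states no longitudinal model or missing-data rule. A week-12 comparison on that basis omits the week-6 values of patients who miss week 12.

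The efficiency gain forgone is about 1 to 5 points of power, for r from 0.5 to 0.8 and half to all dropouts having a week-6 scan. Bias is the stronger reason to change. In the one-arm case at r = 0.7, about 0.24 s is 30% of the planned effect (0.24/0.8) and the 0.44 s limit is 55% (0.44/0.8). Both assume that every dropout was scanned at week 6. The sign depends on which arm loses its poor responders.

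This is a change that should be made; it is not a fatal flaw. The week-12 framing is itself an assumption, because the plan never says which visit is primary. That has to be settled in the same amendment.

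**What to change.** In section 11.2:
- Make the primary analysis of reflux time a mixed model for repeated measures of change at weeks 6 and 12. Include arm, visit, arm-by-visit interaction and the Visit 1 value, with unstructured covariance, in all randomised patients with at least one follow-up Doppler.
- Name one visit's arm contrast as primary.
- Use the same model for the continuous secondary outcomes.
- Keep the t-test and Wilcoxon test as sensitivity analyses, with the Wilcoxon covering non-normality.
- Add one simple sensitivity analysis for departures from missing-at-random, for example shifting the imputed week-12 values of dropouts by a range of amounts in each arm.

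The cost is SAP wording and a standard procedure in SAS, which the plan already uses. No extra patients, visits or scans are needed. The downside is reliance on missing-at-random and on approximately normal residuals. Patients lost before week 6 are not recovered by this change.
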